Appendix D. National Cholesterol Education Program (NCEP) Adult Treatment

- LDL cholesterol (< 3.36, \geq 3.36 and < 4.14, \geq 4.14 mmol/L)
- HDL cholesterol (< 1.03, \geq 1.03 mmol/L)
- Total cholesterol (< 5.17, \geq 5.17 and < 6.21, \geq 6.21 mmol/L)
- Triglycerides (< 1.69, \geq 1.69 and < 2.26, \geq 2.26 mmol/L)

Appendix E. Random Seeds

In case of non-convergence, the random seed will be updated by adding 100000 at each attempt until convergence of model happens. (FSFV: 2019-03-06, 21614; LSFV: 2020-05-05, 22040)

A. Random Seeds for NRI-C

Endpoints	Random Seed	
	MCMC Procedure	PROC MI
All EASI related endpoints	21614	22040
Worst Pruritus NRS improvement ≥ 4	21615	22041

Appendix F. Non-Responder Imputation Incorporating Multiple Imputation to Handle Missing Data Due to COVID-19 Pandemic for Dichotomized Outcome Variables**1.0 Overview****1.1 Background and Justification for Missing at Random (MAR) Assumption**

The COVID-19 pandemic is interfering with the conduct of many ongoing trials, with potential impacts on treatment duration and the collection, analysis and the interpretation of clinical trial data. Some protocol-specified visits in the clinical trials may be impacted due to COVID-19 infection or logistical restrictions during the pandemic. For example, some scheduled visits may be missed due to self-quarantine or local government restrictions on travel; some visits may also be delayed or canceled due to healthcare resource constraints during the pandemic. Impacted visits due to COVID-19 will be recorded in the database. The probability of having missed visits and missing data due to COVID-19 infection or logistical restrictions related to the COVID-19 pandemic can be reasonably assumed to be unrelated to the unobserved values. Therefore, for the purpose of statistical analysis, it is reasonable to assume that these missing data are missing at random (MAR) and the statistical models that require MAR assumption are appropriate. In some cases, sensitivity analyses may be performed to assess the impact of missing data and the robustness of the conclusion.

1.2 FDA Guidance

FDA provided guidance¹ in March 2020 on the efficacy collection and possible changes in the statistical analysis plan:

- "With respect to efficacy assessments, FDA recommends consultation with the appropriate review division regarding protocol modifications for the collection of efficacy endpoints, such as use of virtual assessments, delays in assessments, and alternative collection of research-specific specimens, if feasible. For individual instances where efficacy endpoints are not collected, the reasons for failing to obtain the efficacy assessment should be documented (e.g.,

identifying the specific limitation imposed by COVID-19 leading to the inability to perform the protocol-specified assessment)."

- "If changes in the protocol will lead to amending data management and/or statistical analysis plans, the sponsor should consider doing so in consultation with the applicable FDA review division. Prior to locking the database, sponsors should address in the statistical analysis plan how protocol deviations related to COVID-19 will be handled for the prespecified analyses."

1.3 EMA Guidance

EMA provided guidance¹ in March 2020:

- "At this point in time it is not possible to give general applicable advice on how the different aspects related to the pandemic should be handled, as implications on clinical trials are expected to be manifold. Impact on the data collection, analysis and interpretation of results for each trial will need a thorough case-by-case assessment."
- "As a general principle, there are strong scientific reasons to conduct trials as planned and implement changes only when there is a convincing scientific reason that it improves interpretability of results."

1.4 Missing Data Handling for Missing Due to COVID-19 for Dichotomized Variables

In this document, a missing data handling method is proposed to handle missing data due to COVID-19 infection or logistical restrictions related to the COVID-19 pandemic under the general MAR framework. In particular, we explain using multiple imputation (MI) to handle missing data due to COVID-19 in dichotomized variables in conjunction with non-responder imputation (NRI) for missing data due to other reasons.

2.0 Non-responder Imputation Incorporating Multiple Imputation (NRI-C)

2.1 Overall Description of the Method

For a dichotomized outcome variable with missing data, the NRI-C will categorize any subject who does not have evaluation during a pre-specified visit window as a non-responder for the visit, with two exceptions:

- If the subject is a responder both before and after the pre-specified visit window, the subject will be categorized as a responder for the visit.
- If the reason for missing (e.g., missed visits, incomplete visit, out-of-schedule visits, or discontinuations of study drug) is due to COVID-19, the information will be captured in the database and the subject's response status will be imputed using multiple imputation.

Of note, all assessments after the start of rescue medication will be set as missing before imputation. As a result, these assessments will not contribute to the imputation and the subjects will be counted as non-responders for the analysis. In addition, subjects whose change/percent change from Baseline cannot be calculated because of a missing Baseline will be considered as a non-responder at all post-baseline visits.

Non-responder imputation incorporating multiple imputation (NRI-C) for missing due to COVID-19 will be implemented as follows.

2.2 Multiple Imputation (MI) and MAR Assumption

When a dichotomized variable is derived from a continuous scale, for example, EASI 75 (at least a 75% reduction in EASI relative to Baseline), the multiple imputation will be applied to the original scale, EASI (ranges from 0 – 72) assuming multivariate normal distribution. Then the dichotomized variable will be derived from the imputed value.

The MI procedure assumes that the data are missing at random (MAR). That is, for an outcome variable Y, the probability that an observation is missing depends only on the

observed values of other variables, not on the unobserved values of the outcome variable Y. Statistical inference from the MI procedure is valid under the MAR assumption.

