8.4 Secondary Efficacy Analyses

8.4.1 Key Secondary Efficacy Analyses

The secondary endpoints for the primary analysis of efficacy are:

- Percent change in Worst Pruritus NRS from baseline to Week 16

- Proportion of subjects achieving at least a 100% reduction in Eczema Area and Severity Index from Baseline (EASI 100) at Week 16;
- Proportion of subjects achieving at least a 90% reduction in Eczema Area and Severity Index from Baseline (EASI 90) at Week 16;
- Percent change in Worst Pruritus NRS from Baseline to Week 4;
- Proportion of subjects achieving a 75% reduction in EASI (EASI 75) from Baseline at Week 2;
- Percent change in Worst Pruritus NRS from Baseline to Week 1
- Proportion of subjects achieving an improvement (reduction) in Worst Pruritus NRS ≥ 4 from Baseline at Week 16

Hypotheses corresponding to the endpoints are:

- The percent change in Worst Pruritus NRS from baseline in subjects treated with upadacitinib for Atopic Dermatitis is greater than that of dupilumab at Week 16.
- The proportion of subjects with EASI 100 treated with upadacitinib for Atopic Dermatitis is greater than that of dupilumab at Week 16.
- The proportion of subjects with EASI 90 treated with upadacitinib for Atopic Dermatitis is greater than that of dupilumab at Week 16.
- The percent change in Worst Pruritus NRS from baseline in subjects treated with upadacitinib for Atopic Dermatitis is greater than that of dupilumab at Week 4.
- The proportion of subjects with EASI 75 treated with upadacitinib for Atopic Dermatitis is greater than that of dupilumab at Week 2.
- The percent change in Worst Pruritus NRS from baseline in subjects treated with upadacitinib for Atopic Dermatitis is greater than that of dupilumab at Week 1.
- The proportion of subjects with an improvement (reduction) in Worst Pruritus NRS ≥ 4 with upadacitinib for Atopic Dermatitis is greater than that of dupilumab at Week 16.

Secondary efficacy endpoints will be analyzed by comparing upadacitinib treatment group and dupilumab. The categorical endpoints and continuous endpoint will be analyzed by CMH and MMRM, respectively, and the corresponding analyses are specified in Section 8.1.

Worst Pruritus NRS will be analyzed based on weekly rolling averages of daily scores.

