2.3 Imputation Algorithm

It is reasonable to assume the missing values of the longitudinal data for an outcome variable (e.g., EASI, the original scale of EASI 75, at each post-baseline visit) follows a monotone missing pattern. In practice, the missing data of the outcome variable might have an arbitrary (non-monotone) missing data pattern. An extra step may be added accordingly, to augment data into a monotone missing pattern.

For the outcome variable (e.g., EASI at each visit), K 'complete' datasets can be generated in two steps: augmentation step and imputation step. K, the number of repetitions, is determined below.

Augmentation Step

For datasets with non-monotone missing data pattern, the augmentation step will first impute enough values to augment the data into a monotonic missing pattern:

Markov Chain Monte Carlo (MCMC) will be applied to augment the data using PROC MI with the MCMC IMPUTE=monotone statement, assuming a multivariate normal distribution. The augmented data will be used in the subsequent imputation step to generate 'complete' datasets. Covariates included in the model are treatment, stratification factors (vIGA-AD categories), gender, Baseline, and all post-baseline visits of the outcome variable according to the pre-specified order. Of note, categorical variables are included using the form of dummy variables.

Repeat the imputation process K=30 times using the procedure described above to form K=30 monotone missing datasets, where K is determined as described in "Repetition of imputations (K)."

Imputation Step

For missing data with monotone missing patterns, the choice of multiple imputation using a parametric regression model that assumes multivariate normality is appropriate.

The imputation step is described below:

- The imputation model for the missing data is a regression model, which controls for treatment, stratification factors (vIGA-AD categories), gender, Baseline, and all post-baseline visits of the outcome variable. The covariates included in the model and the order of these variables are consistent with the augmentation step.
- For each monotone missing dataset, using SAS PROC MI with MONOTONE REG model statement, the outcome variable at each post-baseline visit with missing values will be imputed sequentially with covariates constructed from their corresponding sets of preceding variables.

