3.0 Sample SAS Code

```
/*IMPUTATION STEP – DETERMINE IMPUTATION DISTRIBUTION AND RANDOMLY
IMPUTE MISSING VALUE TO GENERATE 'COMPLETE' DATASETS*/
/*****************/
PROC MI DATA=EASI_MONO OUT=EASI_FULL NIMPUTE=1 SEED= 22040 /*RANDOM
SEED PRE-DEFINED*/
    ROUND=. . . 0 1 0 1 0 1 0 1 0 1 0 1 0 1 0 1 0 1 0 1 /*VALUE ROUND TO 1ST
DECIMAL*/
    MIN=. . . 0 0 0 0 0 0 0 0 0 0 0 0 0 0 0 0 0 0 0 0 0 0 /*MINIMUM VALUE OF EASI IS
0*/
    MAX=. . . 72 72 72 72 72 72 72 72 72 72 72 72 72 72 72 72 72 72 72 72 72 72 /*MAXIMUM VALUE OF EASI IS
72*/
    MINMAXITER=1000;
    CLASS TRT01PN VIGAN SEXN;
    VAR TRT01PN VIGAN SEXN BASE WK1 WK2 WK4 WK8 WK12 WK16 WK20 WK24;
    MONOTONE REG (WK1 WK2 WK4 WK8 WK12 WK16 WK20 WK24); /* IMPUTED
SEQUENTIALLY, FROM WK 1 TO 24, WITH COVARIATES CONSTRUCTED FROM THE
CORRESPONDING PRECEDING VARIABLES*/
    BY _IMPUTATION_; /*FOR EACH OF THE 30 MONOTONE
MISSING DATASETS, IMPUTE A 'COMPLETE' DATASET*/
RUN;

/*DETERMINE DICHOTOMOUS RESPONSE STATUS, EASI 75*/
DATA ALL; SET EASI_FULL;
    IF 0<=WK1<=0.25*BASE THEN EASI75_1=1;
    ELSE EASI75_1=0;
    IF 0<=WK2<=0.25*BASE THEN EASI75_2=1;
    ELSE EASI75_2=0;
    IF 0<=WK4<=0.25*BASE THEN EASI75_4=1;
    ELSE EASI75_4=0;
    IF 0<=WK8<=0.25*BASE THEN EASI75_8=1;
    ELSE EASI75_8=0;
    IF 0<=WK12<=0.25*BASE THEN EASI75_12=1;
    ELSE EASI75_12=0;
    IF 0<=WK16<=0.25*BASE THEN EASI75_16=1;
    ELSE EASI75_16=0;
    IF 0<=WK20<=0.25*BASE THEN EASI75_20=1;
    ELSE EASI75_20=0;
    IF 0<=WK24<=0.25*BASE THEN EASI75_24=1;
    ELSE EASI75_24=0;

RUN;

/*****************/
/*
/*          DATA HANDLING STEPS TO MERGE COVID-19 STATUS OMITTED
*/
```

```

/*
   PLACE TO ADD DATA HANDLING AND MERGING STEPS
*/
*****

/*FOR MI, SKIP THE FOLLOWING CODE, PROCEED TO THE CODE AFTER ANALYSIS
MODEL *//*OVERRIDE MISSING VALUES NOT DUE TO COVID-19 WITH TRADITIONAL
NRI*/
DATA ALLF; SET ALL;
  /*COVID19_XX='Y' IF MISSING AT WEEK XX IS DUE TO COVID-19; IF NOT,
OVERRIDE WITH TRADITIONAL NRI*/
  IF COVID19_1 NE 'Y' THEN EASI75_1=EASI75NRI_1;
  IF COVID19_2 NE 'Y' THEN EASI75_2=EASI75NRI_2;
  IF COVID19_4 NE 'Y' THEN EASI75_4=EASI75NRI_4;
  /*VARIABLE EASI75NRI XX: TRADITIONAL NRI DATA AT WEEK XX, WHICH COVERS
THE SPECIAL HANDLING SUCH AS THE BEFORE-AND-AFTER EXCEPTION*/
  IF COVID19_8 NE 'Y' THEN EASI75_8=EASI75NRI_8;
  IF COVID19_12 NE 'Y' THEN EASI75_12=EASI75NRI_12;
  IF COVID19_16 NE 'Y' THEN EASI75_16=EASI75NRI_16;
  IF COVID19_20 NE 'Y' THEN EASI75_20=EASI75NRI_20;

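### Imputed EASI values almost never equal 0, so the multiple-imputation analyses cannot credit EASI 100 responders; EASI 90 and, in proportion less so, EASI 75 are probably understated among imputed subjects too

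*SAP*

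**What the plan says.** SAP Appendix F sets out the imputation. Section 2.2 says that for a dichotomised endpoint such as EASI 75 "the multiple imputation will be applied to the original scale, EASI" (range 0–72), "assuming multivariate normal distribution. Then the dichotomized variable will be derived from the imputed value".

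Section 2.3 has two steps. An MCMC augmentation step first fills enough gaps to make the missing pattern monotone. A sequential regression then fills the rest, for which the SAP says "the choice of multiple imputation using a parametric regression model that assumes multivariate normality is appropriate".

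Section 3.0 prints code for the second step only. It uses MONOTONE REG, rounding to one decimal, a lower limit (the comment reads "MINIMUM VALUE OF EASI IS" 0), an upper limit of 72, and "MINMAXITER=1000".

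The reach of this imputation is as follows.

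- Appendix E assigns its NRI-C seeds to every EASI endpoint.
- SAP 8.2.1 sends COVID-19-related missing values to MI within NRI-C, the primary approach.
- SAP 8.1.1 and 8.2.1 add MI as a sensitivity analysis for the primary and the key secondary categorical endpoints. A comment in the sample code shows that this analysis uses the same imputed data and only skips the non-responder override.
- One of those endpoints, second in the ranked order, is "Proportion of subjects achieving at least a 100% reduction in Eczema Area and Severity Index from Baseline (EASI 100) at Week 16" (SAP 8.4.1).

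The SAP argues for missing at random. It offers no transformation, matching or other allowance for skew or for a mass of subjects at 0.

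**The concern.** A normal distribution puts no probability on any single value, whereas EASI 100 is the event that EASI equals exactly 0. Under this model an imputed subject can become an EASI 100 responder only when a draw happens to fall in the narrow band that rounds to 0.0.

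EASI on treatment is also likely to be crowded near the floor. That is an inference from three facts in the documents: the scale stops at 0, the mean change on upadacitinib 30 mg in Phase 2 was −74.4% (Protocol 4.2), and EASI 100 was chosen as an endpoint. If it is right, a symmetric model truncated at 0 places too many imputed values too high and understates the stricter response thresholds.

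Section 2.2 says that MI inference is valid under missing at random. It also needs an imputation model that fits. What is at stake is whether the MI sensitivity analysis says anything about ranked secondary 2, and whether COVID-missing EASI responses in the primary approach are imputed without bias.

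**Working it through.** **Step 1: the plan's own figure, as a yardstick.** SAP 2.4 assumes 50% against 62%, 325 per arm, two-sided 0.05, and claims more than 80% power.

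- Null SE = √(2 × 0.56 × 0.44 / 325) = 0.0389.
- Alternative SE = √((0.50 × 0.50 + 0.62 × 0.38) / 325) = 0.0387.
- Power = Φ((0.12 − 1.96 × 0.0389) / 0.0387) = Φ(1.13) = 87.1%.

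The claim is reproduced. The documents give no figure for imputation error.

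**Step 2: chance that a bounded draw becomes EASI 0.** With rounding to 0.1, only draws in [0, 0.05) round to 0. The iteration limit is read as redrawing out-of-range values, that is, a truncated normal. For predicted value μ and residual SD s (the upper limit of 72 is negligible here):

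P = [Φ((0.05 − μ)/s) − Φ(−μ/s)] / [1 − Φ(−μ/s)]

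For μ = 2 and s = 3: (0.2579 − 0.2525) / 0.7475 = 0.72%.

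| Predicted EASI | SD 3 | SD 5 | SD 8 |
|---|---|---|---|
| 2 | 0.72% | 0.56% | 0.40% |
| 5 | 0.18% | 0.29% | 0.28% |
| 8 | 0.02% | 0.12% | 0.18% |

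Even a subject predicted at exactly 0 gets only 1.3% (SD 3) to 0.5% (SD 8). These μ and s values are assumptions.

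**Step 3: simulated rates among imputed subjects.** Trials of 650 were generated with a skewed Week 16 EASI and a mass at 0. Week 16 was deleted at random and imputed from treatment, vIGA-AD, sex, baseline and earlier visits, with bounds and rounding as in the code. Eight data models were used (four log-normal, four scaled-beta). All distributional settings are assumptions. Three cases at 5% missing, as dupilumab / upadacitinib in %:

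| Case | Endpoint | True | Imputed |
|---|---|---|---|
| Mild skew, high visit correlation | EASI 75 | 49.7 / 60.3 | 46.4 / 55.9 |
| | EASI 90 | 21.6 / 30.5 | 16.8 / 22.5 |
| | EASI 100 | 3.4 / 7.4 | 0.2 / 0.4 |
| Stronger skew, high correlation | EASI 75 | 53.8 / 65.5 | 44.3 / 53.2 |
| | EASI 90 | 36.9 / 49.8 | 18.5 / 23.8 |
| | EASI 100 | 19.0 / 29.2 | 0.3 / 0.3 |
| Log-normal | EASI 75 | 48.7 / 62.1 | 20.4 / 27.0 |
| | EASI 90 | 26.7 / 37.4 | 7.5 / 10.3 |
| | EASI 100 | 7.0 / 14.2 | 0.1 / 0.2 |

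Across all eight models imputed EASI 100 was 0.1% to 0.6%, against true rates of about 0.2% to 34%. EASI 75 and EASI 90 were understated in every model. The proportional loss is larger for EASI 90. In the upadacitinib arm with mild skew it is 8.0/30.5 = 26%, against 4.4/60.3 = 7% for EASI 75.

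**Step 4: effect on the tested difference.** With the same missing share m in both arms:

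shift ≈ m × [(imputed − true) upadacitinib − (imputed − true) dupilumab]

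Stronger skew, m = 5%:

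- EASI 75: 0.05 × (−12.3 + 9.5) = −0.14 points (simulated −0.13).
- EASI 90: 0.05 × (−26.0 + 18.4) = −0.38 (simulated −0.37).
- EASI 100: 0.05 × (−28.9 + 18.7) = −0.51 (simulated −0.53).

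Over all models at 5% missing, the simulated shifts were about −0.05 to −0.6 (EASI 75), −0.15 to −0.9 (EASI 90) and 0 to −0.9 (EASI 100). At 15% missing with stronger skew they were −0.31, −0.94 and −1.54.

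When the imputed EASI 100 rate is close to 0 in both arms, the shift is about −m times the true difference. That is what plain non-responder imputation gives.

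**Step 5: against the yardstick.** Taking the worst EASI 75 shift at 5% missing, 12.0 − 0.6 = 11.4 points. With the same SEs, power = Φ((0.114 − 1.96 × 0.0389) / 0.0387) = Φ(0.97), about 83%, still above 80%.

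**The case against.** The strongest reply is that the effect on the treatment comparison is small and conservative. Only COVID-missing values are imputed in NRI-C, rescued subjects count as non-responders regardless, and NRI-NC covers EASI 100 without using this imputation at all. This stands. A reader might infer from the large errors among imputed subjects that the primary EASI 75 result is unreliable. Steps 4 and 5 do not support that.

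A second reply is that the documents nowhere give the EASI distribution, the visit correlation or the missing share. This also stands, and it is why the EASI 75 and EASI 90 sizes are shown as a range. The EASI 100 result depends far less on these, because it follows from the width of the rounding band.

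Third, SAP 8.4.2 names only NRI-NC as sensitivity analysis for the binary secondary endpoints. But 8.1.1 and 8.2.1 expressly include the key secondary categorical endpoints in MI.

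Fourth, the bounds appear only in sample code, and the augmentation code is not printed. A missed Week 16 followed by an observed visit is filled in that step. If it is unbounded, 6% to 24% of simulated draws were negative, and the printed EASI 75 rule scores a negative value as non-response. EASI 100, scored in the same way, stayed below 1%, and EASI 75 and EASI 90 fell further. The conclusion therefore does not hinge on the bounds.

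A reader might also infer that the code's list, "VAR TRT01PN VIGAN SEXN BASE WK1 WK2 WK4 WK8 WK12 WK16 WK20 WK24", wrongly omits EASI visits. Protocol 5.5 treats Weeks 4, 8 and 12 as consecutive scheduled visits for EASI, which agrees with the list, so no such claim is made.

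**Conclusion.** The point holds in a limited form.

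- **EASI 100.** The planned imputation gives a value of 0 with probability below about 1% over the predicted values considered. The MI sensitivity analysis for ranked secondary 2 therefore collapses towards non-responder imputation and is not an independent check. COVID-missing EASI 100 in NRI-C is understated to the extent that some of those subjects would truly have scored 0.
- **EASI 90 and EASI 75.** If on-treatment EASI is right-skewed near 0, both are understated among imputed subjects even when missing at random holds, EASI 90 more so in proportion. The amount depends on quantities that the documents do not give.
- **Primary test.** It is not threatened. The simulated whole-trial shift was under 1 point at 5% missing for every EASI endpoint, mostly towards no difference. That direction rests on equal missing shares in the two arms. For EASI 100 it would reverse only if missing share times true rate were larger for dupilumab than for upadacitinib.

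**What to change.** Replace both the MCMC augmentation step and the MONOTONE REG step with a single method that respects the EASI distribution and handles non-monotone gaps. PROC MI with FCS REGPMM (predictive mean matching) would do this, with the same covariates, K=30 and no MIN or MAX. Imputed values are then observed EASI values, zeros included. Changing only MONOTONE REG to its matching version would leave every value filled in the augmentation step uncorrected, including a missed Week 16 with a later visit observed. The rescue and non-responder overrides stay as they are.

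In the log-normal simulations, matching brought imputed rates to within about 3 points of the truth in nearly all cells. In the log-normal case tabulated above, EASI 75/90/100 came to 49.2/26.1/7.8 (dupilumab) and 62.7/39.3/14.7 (upadacitinib). That check covered a missing Week 16 imputed from earlier visits. The FCS form and the scaled-beta models were not tested with matching.

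The cost is a small edit to Appendix F (2.2, 2.3 and 3.0), with matching changes to the MI description in SAP 8.2.1 and the seed table in Appendix E. No new data are needed. Imputed results will change slightly.

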2.3 Imputation Algorithm

It is reasonable to assume the missing values of the longitudinal data for an outcome variable (e.g., EASI, the original scale of EASI 75, at each post-baseline visit) follows a monotone missing pattern. In practice, the missing data of the outcome variable might have an arbitrary (non-monotone) missing data pattern. An extra step may be added accordingly, to augment data into a monotone missing pattern.

For the outcome variable (e.g., EASI at each visit), K 'complete' datasets can be generated in two steps: augmentation step and imputation step. K, the number of repetitions, is determined below.

Augmentation Step

For datasets with non-monotone missing data pattern, the augmentation step will first impute enough values to augment the data into a monotonic missing pattern:

Markov Chain Monte Carlo (MCMC) will be applied to augment the data using PROC MI with the MCMC IMPUTE=monotone statement, assuming a multivariate normal distribution. The augmented data will be used in the subsequent imputation step to generate 'complete' datasets. Covariates included in the model are treatment, stratification factors (vIGA-AD categories), gender, Baseline, and all post-baseline visits of the outcome variable according to the pre-specified order. Of note, categorical variables are included using the form of dummy variables.

Repeat the imputation process K=30 times using the procedure described above to form K=30 monotone missing datasets, where K is determined as described in "Repetition of imputations (K)."

Imputation Step

For missing data with monotone missing patterns, the choice of multiple imputation using a parametric regression model that assumes multivariate normality is appropriate.

The imputation step is described below:

- The imputation model for the missing data is a regression model, which controls for treatment, stratification factors (vIGA-AD categories), gender, Baseline, and all post-baseline visits of the outcome variable. The covariates included in the model and the order of these variables are consistent with the augmentation step.
- For each monotone missing dataset, using SAS PROC MI with MONOTONE REG model statement, the outcome variable at each post-baseline visit with missing values will be imputed sequentially with covariates constructed from their corresponding sets of preceding variables.
- A 'complete' dataset with imputed values for the missing data is generated after the augmentation and imputation steps are completed.

Repetition of Imputations (K)

Repetition of imputations, K, must be determined in advance. When estimating the overall variance of multiple imputation, the additional sampling variance is the between-imputation variance divided by K. This value represents the sampling error associated with the overall or average coefficient estimates. It is used as a correction factor for using a specific number of imputations. The more imputations (K) are conducted, the more precise the parameter estimates will be. For example, with a 1% power falloff tolerance in multiple imputation, as compared to an infinite number of imputations, multiple imputation requires 20 repetitions of imputation for 30% missing information and 40 repetitions for 50% missing information (Graham, Olchowski, and Gilreath 2007).² In the usual clinical settings expecting less than 30% missing information, K=30 repetitions are deemed sufficient. When missingness exceeds 30%, depending on the power falloff tolerance level, number of repetitions may need to be increased. Recent research

suggested that the number of repetitions (K) should be at least equal to the percentage of missing (White et. al., 2011).⁴

